2. LAY SUMMARY

A malignant pleural effusion (MPE) is a buildup of fluid around the lungs due to any type of cancer that has either started or spread to the lining of the lungs (pleura). This is a very common problem, effecting over 100 people per day in the UK. Typically, people with MPE experience debilitating breathlessness due to fluid buildup. Another challenge for people suffering with MPE is the challenge to reach a diagnosis which can delay treatment with, for example chemotherapy.

At present, in the standard investigation and management pathway for patients with a pleural effusion suspected to be due to cancer, patients have some fluid drawn off and the cells analysed for the presence of cancer cells. This often is not successful and recent data from our site has suggested only 20% of patients receive enough information from fluid alone to treat their cancer. The patient therefore has to come back for a biopsy of the lining of the lung. Once a diagnosis is secured, steps to stop the fluid around the lungs coming back are taken, one of which is to insert a long-term tube in the chest (indwelling pleural catheter, IPC) which is dressed and can be used a few times per week to let fluid out (done by a district nurse or carer at home). Typically, with the current pathway, patients wait 6 weeks for a diagnosis and over 2 months for long term control of breathlessness. Many of these patients have a life expectancy of 3-12 months and as such a large proportion of this is spent breathless and without a diagnosis.

We aim to create a new accelerated pathway (diagnosing and managing fluid build up, which is all part of standard care) for patients suffering with potential MPE, such that at their first visit, patients will be offered a biopsy which give them the highest likelihood (80-95% success rate), of reaching a diagnosis and in the same (first) visit, the patients will have a long term chest tube fitted (indwelling pleural catheter, IPC) so they are not left breathless and needing multiple procedures. This could achieve diagnosis and treatment in one procedure rather than multiple separate procedures in the standard pathway.

Our study will randomise patients in to either a group having the current standard care pathway, or into the accelerated pathway. We will assess key parameters such as the time to diagnosis, overall duration of breathlessness while awaiting a diagnosis, and quality of life.

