Randomised trials to date in MPE have compared definitive treatments, e.g. talc pleurodesis with indwelling pleural catheter^{7 8}. However, these interventions were implemented **after the initial diagnostic pathway** and **do not capture** the need for multiple procedures leading up to this point, or the frequent breathlessness patients experience until definitive fluid management.

Great progress has been made in other areas of care (e.g. lung cancer) to speed up diagnostics (target 14 days) and treatment, with current guidelines advocating early CT scanning, and a 'direct to biopsy' approach⁹. We aim with this research to bring the much slower MPE pathway in line with similar rapid cancer pathways.

Why do we need a clinical study to demonstrate feasibility and patient benefit?

High quality evidence is required to demonstrate that the new pathway is acceptable to patients and provides demonstrable positive impact on quality of life. The proposed STREAMLINE pathway includes invasive interventions such as pleural biopsy and indwelling pleural catheter insertion as a first procedure. This represents significant impact on patients' day to day life and it is essential to capture the potential benefits to breathlessness and time to diagnosis versus the potential psychological and physical impact of a long term pleural catheter and a more invasive first procedure. There is a risk of a small number of patients receiving a therapeutic intervention targeted to malignant pleural effusion that receive a final diagnosis that is not cancer.

Benefits to healthcare

UK data has shown that IPCs are more cost effective than talc pleurodesis¹⁰ in the definitive management of MPE in patients with <14 weeks survival. Other studies have shown that inpatient management of pleural effusion can cost up to seven times that of outpatient management¹¹. In addition, these studies were conducted prior to the COVID-19 pandemic, and in our semi-structured interviews with patients on the MPE pathway, the majority were keen to avoid inpatient admission and the associated risks. The benefit of avoiding emergency admission (a common occurrence within the current MPE pathway) cannot be understated in terms of healthcare costs. Finally, earlier control of pleural fluid has the potential to maintain patient's performance status and allow treatment with chemotherapy.

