6. OBJECTIVES AND OUTCOME MEASURES

	Objectives	Outcome Measures			
Primary	Feasibility of recruitment and data collection.	40 patients randomised 1:1 between the standard pathway and accelerated pathway proportion of eligible patients who agree to randomisation / data completeness / availability and participant completion.			
Secondary	 Mean change and standard deviation in breathlessness 	 100mm VAS scores completed before and after the procedure and 3x weekly thereafter for 6 weeks 			
	2. Patient anxiety and depression	 Hospital anxiety and depression score (HADS) weekly for 6 weeks 			
	3. Health Related Quality of Life	3. EQLQ-C30 questionnaire, EQ 5D-5L questionnaire weekly for 6 weeks			
	4. Time to actionable histopathology /diagnosis	4. Cancer multi-disciplinary team consensus			
	5. Healthcare utilisation	5. Number of pleural procedures and days in hospital post enrolment			
	 Assess the acceptability to patients of the accelerated pathway and patient priorities 	 Perform structured qualitative interviews with a proportion of patients in both the standard care arm and accelerated arm and those declining participation. 			
	7. Proportion of adverse events for both arms	7. Record agreed adverse events			

[figure not shown]
Patient group	Patients with suspected malignant pleural disease, based on any of: presentation, imaging, prior asbestos exposure or history of malignancy:
Intervention(s)	First procedure as a pleural biopsy (local anaesthetic thoracoscopy if available or image guided biopsy if local constraints preclude thoracoscopy) AND Indwelling pleural catheter (IPC) insertion in a single procedure = the accelerated pathway
Comparator	Standard care pathway as defined by the current British Thoracic Society Guidelines, with first procedure as pleural aspiration only, followed by subsequent procedures for tissue biopsy and definitive fluid control

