9. PROTOCOL PROCEDURES

The following table illustrates scheduled procedures and data collection

	its						
				Follow up visits			
Procedures/assessments	Screening	Consent / Baseline / Randomisation	Day of Procedure	Week 2	Week 6	Week 12	Adhoc clinical review as requiredy
		Up to -14 days	Day 0	± 3	± 3	± 7	
Eligibility assessment	х	х					
Informed consent		х					
Demographics and Medical History ^R	x	х					
Clinical assessment ^R	х	х	х	х	х		
Observations (vital signs) ^R		х	х	х	х		
Imaging Routine - Thoracic Ultrasound ^R		Х	Х	х	х		
Imaging Routine - Chest X-ray ^{1 R}	х	х	х	х	х		
Imaging Routine – CT Chest ^R	x						
Routine clinical bloods ^R		X ¹¹					
Concomitant medications ^R	х	х		х	х	х	
Randomisation		х					

Clinical Research Protocol Template version 15.0

CONFIDENTIAL

© Copyright: The University of Oxford and Oxford University Hospitals NHS Foundation Trust 2019 Page 20 of 38

IPC insertion		X ¹²				X ₆
Pleural Biopsy		X ¹²				X ⁵
Therapeutic Aspiration		X ²				
IPC drainage information		X ¹²	х	х	х	X ⁷
VAS-Dyspnoea and VAS-Pain		X ³	х	х		
QOL: EQ5D, EORTC QLQ C30, HADS		X ⁴	х	х	х	
Healthcare utilisation			х	х	х	
Adverse event assessments		х	х	х	х	
Time to histological diagnosis and systemic oncological treatment					х	х
Semi-structured interview ⁸				х		х
Trial Nurse telephone call ⁹						х
Ad Hoc Clinical Appointment						х

¹A screening chest X Ray can be used as baseline if conducted within 2 weeks prior to first procedure.

²In standard care arm and as required throughout trial duration

³Self-reported VAS scores measured pre-and post procedure, 3 x per week from Day 0 to week 6

⁴Measured pre-procedure and 1/week for 6 weeks

⁵As required as part of 'standard care' arm

⁶As determined by patient and clinician choice in 'standard care arm', typically after confirmed histological diagnosis

⁷3 x per week

⁸ At or after week 6 appointment

⁹Intermittently during the six weeks post intervention to ensure diary completion

¹⁰ Patients may require urgent reviews or procedures due to symptoms -these can be delivered at any stage during the study as part of routine care

¹¹ Blood tests carried out up to four weeks prior to the initial procedure are accepted

¹² In accelerated arm only

^RIndicates procedures or data collection that is part of routine care for all patients. The results of these are required to be collected and documented as part of the STREAMLINE study, hence are included in this table.

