9.8. Subsequent Visits

The follow up period is 12 weeks post procedure Trial follow up appointments will take place at

- 2 weeks ± 3 days
- 6 weeks ± 5 days and
- 12 weeks ± 7 days post procedure

This follow up schedule mirrors normal clinical care. Appointments should take place at the patient's local centre.

Data collected at each follow up will be:

1. VAS diary (week 2, 6 visit)

2. QLQ C30, EQ 5D 5L, and HADS diary (week 2, 6 visit)

3. Side effects attributable to the trial intervention

4. Information on healthcare utilisation including inpatient and outpatient admissions for pleural effusion management and any other cause

5. Ultrasound and Chest X Ray will be conducted at 2 weeks and 6 weeks as part of standard care, and results documented on the CRF.

At each follow up visit participants will undergo a standard clinical consultation, which should be conducted by a medical member of the trials team and the appropriate CRF should be completed. A chest x-ray (and ultrasound if available) should be performed (as per routine clinical care) and the results entered into the CRF. Participant completed diaries will be reviewed at these visits.

Participants will be asked to complete a home VAS diary three times per week and Quality of Life scores (1 per week) for 6 weeks post index procedure.

In light of the COVID-19 pandemic it is possible that participants and/or sites will judge that participant contact should be minimised. In recognition of this, follow up visits at 12 weeks may be carried out remotely via telephone.

Reasonable travel expenses to participants for visits that do not align with clinical care will be covered as part of the per participant costs. All feasible efforts have been made to align clinical and study visits, however, 'non-aligned' visits may occur in cases, for example whereby participants have required clinical review outside the study visits and thus are required to attend for a study visit sooner than otherwise required.

Visual Analogue Scale (VAS) scoring

VAS outcomes will be captured using participant paper diaries. Following hospital discharge, participants will receive a trial nurse phone call once per week, according to local availability, as a reminder to complete the VAS scores. The schedule of VAS scores is as follows:

• Pre-procedure VAS (day of first procedure, immediately prior).

- Post procedure VAS (day of the procedure, before discharge)

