11.2. Description of the Statistical Methods

Outcome Measures

We will adopt clear criteria for progression to a large-scale clinical study. If all criteria are met (green) we will proceed to apply for future funding for a full clinical study with the same protocol; if one or more

criteria is amber, we will adapt the protocol to address the shortfall and re-assess, and any red criteria will prompt major changes to study design or non-progression.

The major feasibility outcomes are as below (includes all sites) and are to be applied once all centres are actively recruiting:

	Green	Amber	Red
1. Average monthly recruitment	≥1.5	0.5-1.5	<0.5
(pts / month)*			
2. Proportion of data completion	³ 90%	75%-90%	<75%
(VAS, QOL) in those capable of			
completing (i.e. not including			
those who have died during trial			
follow up)			
3. Data availability - time to	≥90%	75%-90%	<75%
diagnosis			
4. Proportion completing study	≥90%	80-90%	<80%
protocol in those who are still			
alive at end of follow up			
5. Proportion of eligible patients	>50%	30-50%	<30%
randomised			

*Once all centres have been greenlighted

In depth screening logs will be maintained at recruiting centres, in order to calculate the proportion of eligible patients and the proportion accepting randomization to the study protocol. A patient is considered to be eligible if they fulfil all of the inclusion criteria and none of the exclusion criteria. Screening logs will be reviewed by the central trial team on a monthly basis once all centres have been greenlighted.

Secondary outcomes:

- Mean change and SD in 100mm visual analogue score for breathlessness. This is the current proposed primary outcome measure for a definitive clinical trial and will be measured over follow up.
- Time to actionable histopathology (MDT consensus, referral for oncological treatment)
- Healthcare utilization number of pleural procedures over 3 months follow up
- Patient anxiety and depression over the diagnostic pathway period (hospital anxiety and depression score (HADS), quality of life by QLQ-C30 tool)
- All-cause mortality (retrospective electronic patient record review)

Data and Statistical Analysis

Feasibility parameters will be analysed for the overall trial and for each individual arm of the trial. The mean / median and variability of each major outcome will be calculated, to power a potential future definitive study.

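### Time to diagnosis has no single event definition, no stated time origin and no rule for patients who die or remain undiagnosed, although it feeds a progression criterion

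*Protocol*

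**What the plan says.** The outcome appears under several wordings in the protocol:

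- Section 6 (and the section 3 synopsis): "Time to actionable histopathology /diagnosis", measured by "Cancer multi-disciplinary team consensus".
- Section 11.2, secondary outcomes: "Time to actionable histopathology (MDT consensus, referral for oncological treatment" (closing bracket not shown).
- Section 9, schedule of procedures: "Time to histological diagnosis and systemic oncological treatment".
- Section 11.2, progression criterion 3: availability of time-to-diagnosis data, with no mention of histology.

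On analysis, section 11.2 says: "The mean / median and variability of each major outcome will be calculated". The only model named is a mixed effects regression for repeated sampling. Section 11.8 reports missing data without adjusting for them. Section 11.1 states that no separate SAP is in use, so section 11 is the whole plan.

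On timing, section 9 sets Day 0 at the procedure and section 9.8 says "The follow up period is 12 weeks post procedure". Section 9.4 lets randomisation take place on the procedure day or up to a week before it. No origin is given for time to diagnosis itself.

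**The concern.** The wordings can give one patient different dates, or no date. A patient whose MDT acts on cytology has an event under section 6 but, on a literal reading, none under the schedule. Section 5 expects that a few participants will "receive a final diagnosis that is not cancer"; they may never be referred to oncology. Nothing says how to treat a patient who dies undiagnosed or is still undiagnosed at week 12, in a population where section 2 puts many at 3 to 12 months' life expectancy.

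Two things are at stake. The summary of this outcome is meant to inform a definitive trial. Criterion 3 is one of five that decide progression, and its value would depend on which wording a site follows and on how undiagnosed patients are scored. Criteria 2 and 4 set deaths aside explicitly; criterion 3 does not.

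**Working it through.** The protocol gives no sample size or power for this outcome, so there is no stated figure to reproduce. Three checks follow.

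**1. How many patients does the wording affect?** Section 5 gives cytology sensitivity of 37–43% and says more than 65% of cytology-positive patients still need a biopsy, so at most 35% do not.

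- 0.37 × 0.35 = 0.13 and 0.43 × 0.35 = 0.15; times 20 per arm gives 2.6 to 3.0 patients (an upper limit on these inputs).
- Section 2 reports that "only 20% of patients receive enough information from fluid alone to treat their cancer": 0.20 × 20 = 4 patients.

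So about 3 to 4 of 20 standard-arm patients have a date that turns on the wording. If they were left out, the mean would shift by (m − p·t)/(1 − p) − m, where m is the overall mean, p the share left out and t their time to diagnosis. The protocol gives no t; 7 to 14 days is assumed. It gives two values of m for the current pathway: 30 days (section 5) and 6 weeks, or 42 days (section 2).

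- m = 30: +2.4 days (p = 0.13, t = 14) to +5.8 days (p = 0.20, t = 7).
- m = 42: +4.2 to +8.8 days.

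**2. What does averaging observed times do?** Assume exponential times to diagnosis (mean m) and to death (median S = 91 or 365 days), cut off at day 84. With h = 1/m, d = ln 2/S and H = h + d:

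- diagnosed by day 84 = (h/H)(1 − e^(−84H))
- mean of observed times = 1/H − 84·e^(−84H)/(1 − e^(−84H))

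For m = 30 and S = 91: H = 0.0333 + 0.0076 = 0.0410; e^(−84H) = 0.032; mean = 24.4 − 2.8 = 21.6 days.

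| True mean (days) | Median survival (days) | Diagnosed by day 84 | Died undiagnosed | Alive undiagnosed | Mean of observed times (days) |
|---|---|---|---|---|---|
| 30 | 91 | 79% | 18% | 3% | 21.6 |
| 30 | 365 | 90% | 5% | 5% | 23.8 |
| 42 | 91 | 70% | 23% | 7% | 25.4 |
| 42 | 365 | 82% | 7% | 12% | 27.9 |

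(Rows may not sum to 100% because of rounding.)

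The observed mean falls short by 6 to 8 days when the true mean is 30, and by 14 to 17 days when it is 42. Taking 30 and 42 as a faster and a slower arm, purely for illustration, a true gap of 12 days appears as 25.4 − 21.6 = 3.8 or 27.9 − 23.8 = 4.1 days.

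**3. Criterion 3.** Green is 90% or more. With 40 patients, 36/40 = 90% is green and 35/40 = 87.5% is amber, so five participants without a date change the colour. Under the assumptions of check 2, 10–30% of 20 standard-arm patients, that is 2 to 6, would be undiagnosed at week 12 or dead before diagnosis. Whether they count as missing is not stated.

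**The case against.** The best defence is that the outcome is clear in substance. Section 5 defines an actionable diagnosis by whether it can guide systemic treatment and itself speaks of actionable cytology. Section 6 allows a diagnosis by MDT consensus, and a cytology-based MDT decision with referral would meet the bracketed wording in section 11.2. The schedule entry is a row label. This is also a secondary outcome in a 40-patient feasibility study, and a median could be taken from a time-to-event curve.

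Much of that stands, and it rules out stronger readings that a reader might infer:

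- **That the protocol excludes cytology diagnoses.** It does not; exclusion needs the strictest reading of two labels against the rest of the text.
- **That the procedure clock favours the accelerated arm.** No origin is stated for this outcome, the one-week allowance applies to both arms, and no waits by arm are given. Seven days against a 30-day mean (23%) is a maximum, not an estimate of bias. Aspiration is the standard arm's index procedure, so its cytology result comes after Day 0 in any case.
- **That four cytology patients cap criterion 3 at 36/40.** This imports histology into a row that does not mention it, and 36/40 is still green.
- **That everything tilts towards the accelerated pathway.** Averaging observed times shortens the slower arm more, which works the other way.

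The defence does not supply one event, an origin, or a rule for death and non-diagnosis. A median from a time-to-event curve would be sound, but the protocol does not say it will be one. With no separate SAP in use, these gaps cannot be left to another document.

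**Conclusion.** The concern holds as an inconsistency in definition with an unsuitable summary, not as a demonstrated bias towards either arm. The event is worded differently in sections 6, 9 and 11.2, the clock has no stated start, and a plain mean of observed times is biased short by roughly 6 to 17 days under exponential times, median survival of 3 to 12 months and true means of 30 to 42 days. The wording matters for about 3 to 4 of 20 standard-arm patients. The shift from leaving them out also rests on an assumed cytology time of 7 to 14 days and pushes the standard-arm mean up, while averaging observed times pulls it down, so the net direction is not established. The consequence that does not depend on direction is criterion 3, whose result can move from green to amber on five patients with no rule for scoring them. The point should be corrected, in proportion to a secondary outcome that feeds a progression decision.

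**What to change.** - **Event.** Use one definition in sections 3, 6, 9 and 11.2: the date of MDT consensus on an actionable diagnosis from any specimen, cytology or histology. Record non-malignant final diagnoses as a separate category, since they may have no oncology referral. Keep the start of systemic treatment as its own date.
- **Origin.** Count from randomisation, in line with the intention-to-treat analysis in section 11.4. Follow-up to 12 weeks after the procedure already reaches 12 weeks after randomisation, visit windows aside.
- **Summary.** Report cumulative incidence of diagnosis to week 12 by arm, with death as a competing event and patients alive and undiagnosed censored. Take the median from that curve. Curves with about 20 per arm will be imprecise, but they use every participant.
- **Criterion 3.** Count a participant as available if the diagnosis date is known, or if undiagnosed status at death or at week 12 is known.

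The cost is a wording change, slightly more analysis work and possibly one CRF field for specimen type (the CRFs are not shown, so this cannot be confirmed).

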11.3. Sample Size Determination

As a feasibility study, sample size has not been formally calculated. However, other feasibility studies looking at interventions in MPE have typically used 30 to 50 participants^{22 23}.

In a potential future definitive study of the accelerated pathway, mean difference in VAS (for which the MCID is 19mm) would be a likely primary outcome measure. In such a study, 170 participants would be sufficient to detect a mean difference of 19mm between the two arms (5% significance, 90% power) assuming an SD of 35mm based on previous MPE studies⁷.

If a quality of life measurement was preferred as the primary outcome, the MCID in global health status based on reference values provided by the EORTC Quality of Life Group is 8 points.190 patients would achieve a 90% power to detect an 8 point difference^{24 25} with a common SD within group of 23.6, derived from EORTC reference values.

Thus, in a future 8-centre study, a recruitment target of 190 patients (powered for VAS or QOL) could be achieved in 18 months if recruitment occurs at approximately 1-2 participants per centre per month. **Therefore, the recruitment target for our proposed feasibility study is 1-2 participants per month.**

We propose 40 patients to allow for 10% attrition and based on likely recruitment rate within the study timetable.

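### On the stated inputs, 190 patients in total give about 64% power for the quality-of-life outcome, not the 90% claimed in section 11.3

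*Protocol*

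**What the plan says.** Section 11.3 sizes a possible future definitive trial in two ways. For breathlessness on the VAS it gives 170 participants for a "mean difference of 19mm between the two arms (5% significance, 90% power"), with the SD taken as 35 mm. For the alternative, quality of life, it says "the MCID in global health status based on reference values provided by the EORTC Quality of Life Group is 8 points" and that "190 patients would achieve a 90% power to detect an 8 point difference". The SD behind that figure is 23.6, common to both groups and taken from EORTC reference data. The quality-of-life sentence states no significance level, sidedness, attrition allowance, baseline adjustment or gain from repeated measurements.

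The next paragraph merges the two figures for a trial in 8 centres: "a recruitment target of 190 patients (powered for VAS or QOL) could be achieved in 18 months", provided that each centre enrols about one to two people a month. The feasibility study's own target of 1-2 participants per month is drawn from that sentence.

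**The concern.** The 8-point difference is about a third of the SD (8/23.6 = 0.34). The VAS difference is over half of its SD (19/35 = 0.54). A standardised effect that much smaller needs well over twice the sample at the same power, yet the quality-of-life figure is only 20 patients larger than the VAS figure. Either 190 is not a total, or it does not give 90% power.

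At stake is the size of a later trial if quality of life were chosen as its primary outcome, and whether the per-centre recruitment rate quoted in section 11.3 would be enough for such a trial.

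**Working it through.** **Inputs.** From section 11.3: difference 8, SD 23.6, power 90%, 8 centres, 18 months. The 5% level is carried over from the VAS sentence ("5% significance, 90% power"). The protocol does not state sidedness; two-sided is assumed. The 1:1 allocation is taken from section 9.4, where it is stated for the feasibility study. The comparison is unadjusted, at one timepoint, with no attrition.

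**Is 190 a total or a per-arm figure?** 8 centres × 18 months = 144 centre-months.
- As a total: 190/144 = 1.32 per centre per month, inside 1-2.
- As per arm: 380/144 = 2.64, outside 1-2.

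So section 11.3 uses 190 as the total.

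**Attempt to reproduce 190.** n per arm = 2 × (1.960 + 1.282)² × (23.6/8)² = 2 × 10.507 × 8.7025 = 182.9, so 183. The t-test gives 183.8, so 184 per arm and 368 in total. The figure does not reproduce as a total.

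**Power of 190 in total (95 per arm).** Standardised difference = 8 / (23.6 × √(2/95)) = 2.336. Normal approximation: Φ(2.336 − 1.960) = 64.7%. The t-test gives 64.2%.

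**What 190 in total would support at 90% power (t-test).** A detectable difference of 11.2 points with SD 23.6, or an SD of about 16.9 with 8 points.

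**190 per arm.** The t-test gives 90.9% power.

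**Other significance levels and power** (normal approximation, totals):

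| Test | Power | Total needed |
|---|---|---|
| Two-sided 5% | 90% | 366 |
| One-sided 5% | 90% | 300 |
| Two-sided 5% | 80% | 274 |
| One-sided 5% | 80% | 216 |

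All exceed 190. A one-sided 5% test with 95 per arm has 75% power.

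**Baseline adjustment.** With ANCOVA the required n is multiplied by (1 − ρ²). For 95 per arm, ρ = √(1 − 95/182.9) = 0.69. Section 11.3 states no correlation.

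**Cross-check on VAS.** With 19 mm and SD 35, the t-test gives 72.3, so 73 per arm and 146 in total. 170 in total gives 94% power before attrition. The VAS figure is adequate as a total.

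**Per-centre rates over 144 centre-months.** VAS: 170/144 = 1.18. Quality of life: 368/144 = 2.56.

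**The case against.** **The power figure depends on the analysis.** Section 9 schedules quality of life before the procedure and weekly for 6 weeks, and section 11.2 plans a mixed effects model. A definitive trial analysed that way could do much better than 64%. As an illustration, take equal correlation ρ between all scores and 95 per arm. The mean of six weekly scores, unadjusted, has variance factor (1 + 5ρ)/6, which gives about 91% power at ρ = 0.4 and 86% at ρ = 0.5. Adjusting also for baseline gives about 98% or more for ρ from 0.2 to 0.9. This stands as a limit: 64% and 368 hold only for an unadjusted single-timepoint comparison. It does not rescue the sentence, because section 11.3 quotes a plain within-group SD and states no correlation, adjustment or averaging.

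**Little in this trial rests on the figure.** This stands. Section 11.3 says the feasibility size was not formally calculated. Section 11.2 names VAS as the proposed primary outcome of the definitive trial and plans to estimate the variability of the major outcomes to power it. The VAS figure alone gives 1.18 per centre per month, so the 1-2 rate survives without the quality-of-life figure. A reader might infer that the error undermines the 40 patients or the recruitment progression criterion; the protocol does not support that. The green threshold of 1.5 per month also covers all sites together, so it is not on the same scale as 2.56 per centre.

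**The origin of 190 is not stated.** A reader might take it as established that 190 is a per-arm number. It fits best, at 91% power, but the per-arm minimum is 183-184. A one-sample calculation (93.4, so 94) doubled to 188 lands just as close. Only the failure as a total is established.

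**Attrition.** The 10% in section 11.3 is stated for the 40 patients only, so it is not applied to the larger trial here.

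**Conclusion.** The concern holds in limited form. Section 11.3 uses 190 as a whole-trial total, and on its stated inputs that gives about 64% power for an 8-point difference, against the 90% claimed. About 184 per arm, 368 in total before attrition, would be needed. The statement that 190 is powered for either outcome is right for VAS only. These figures assume a two-sided 5% test, 1:1 allocation and an unadjusted comparison at one timepoint. None of the significance-level, sidedness or 80%-power variants tried brings the requirement down to 190. A mix-up of per-arm and total is the likely cause but is not shown.

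The consequence is confined to a quality-of-life-primary definitive trial. At 368 patients it would need about 2.6 per centre per month over 8 centres and 18 months, above the stated 1-2. A green recruitment result would therefore not by itself show that such a trial is deliverable on that footprint. The point should be fixed, but it is not critical to this feasibility study.

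**What to change.** Three changes of wording in section 11.3:

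1. Restate the quality-of-life figure as about 184 per arm, 368 in total before attrition, for an unadjusted single-timepoint comparison at two-sided 5%. Alternatively keep 190, and state and justify the baseline or repeated-measures correlation and the analysis that make it sufficient.
2. If the first option is taken, limit the power claim attached to the 190 target to VAS.
3. Give the per-centre monthly rate for each candidate outcome over 8 centres and 18 months: about 1.2 for VAS at 170, and about 2.6 for quality of life at 368. Say that the second lies above the 1-2 range. If an attrition allowance is wanted for the definitive trial, state it and apply it to both.

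The cost is a text correction. The 40 patients, the study procedures and the progression thresholds do not change.
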